### 4.2 Exclusion criteria

The presence of any of the following will exclude a patient from enrolment:

1. Previously *not* exposed to oxaliplatin **and** irinotecan **and** Flouoropyrimidine (5FU or capecitabine) based cytotoxic chemotherapy (prior pelvic radiation therapy including adjuvant or neoadjuvant chemo-radiation therapy for resected rectal cancer is allowed provided it is completed within 4 weeks prior to study entry)
2. Less than 6 months from completion of adjuvant chemotherapy to diagnosis or documentation of recurrent cancer

3. Palliative radiotherapy to non-target, metastatic lesions will be allowed provided it was completed within 4 weeks prior to study entry.
4. Prior surgery within 4 weeks prior to study entry
5. Current treatment within another therapeutic clinical trial.
6. Presence of grade  $\geq 2$  peripheral neuropathy.
7. Grade  $\geq 2$  thrombocytopenia (i.e., platelet count  $< 75,000/\mu\text{L}$ ), grade 3 neutropenia (i.e., absolute neutrophil count  $< 1500/\mu\text{L}$ ), or grade 3 non-hematologic adverse event associated with prior adjuvant oxaliplatin, irinotecan and/or 5-FU treatment.
8. History of significant bleeding within the past 3 months, including gross haemoptysis or haematuria, or underlying coagulopathy.
9. History of abdominal fistula, gastrointestinal perforation, or intra-abdominal abscess within 3 months prior to study enrolment, unless affected area has been removed surgically.
10. On-going cardiac dysrhythmias of grade  $\geq 2$ , atrial fibrillation of any grade, or QTc interval to  $> 450$  msec for males and  $> 470$  msec for females.
11. Hypertension uncontrolled by medication ( $> 150/100$  mmHg despite optimal medical therapy).
12. On-going treatment with therapeutic doses of warfarin (however, low dose warfarin up to 2mg daily for deep vein thrombosis prophylaxis is allowed). Low molecular weight heparin (LMWH) is allowed.
13. Diagnosis of any second malignancy within the last 3 years that is potentially liable to interfere with study outcomes (basal cell carcinoma, squamous cell skin cancer, or in situ carcinoma and hormone controlled locally advanced prostate cancer that has been adequately treated with no evidence of recurrent disease for 12 months, are allowed)
14. History of or known brain metastases, spinal cord compression, or carcinomatous meningitis, or new evidence of brain or leptomeningeal disease on screening CT or MRI scan.
15. Known human immunodeficiency virus (HIV) infection.
16. Pregnancy, breastfeeding, or unwillingness/inability to employ an effective method of birth control/contraception to prevent pregnancy during treatment and for up to 3 months after discontinuing study drug if of reproductive potential.
17. Other severe acute or chronic medical or psychiatric condition, or laboratory abnormality that would impart, in the judgement of the investigator, excess risk associated with study participation or study drug administration, or which, in the judgment of the investigator would make the patient inappropriate for entry into the trial.
18. Gastrointestinal abnormalities including: inability to take oral medication; requirement for intravenous alimentation; prior surgical procedures affecting absorption; treatment for active peptic ulcer disease in the past 6 months; active gastrointestinal bleeding, unrelated to cancer, as evidenced by hematemesis or melaena in the past 3 months without evidence of resolution documented by endoscopy or colonoscopy;
19. Current use or anticipated need for treatment with drugs that are known CYP3A4 or CYP1A2 inducers (i.e. carbamazepine, dexamethasone, felbamate, omeprazole, phenobarbital, phenytoin, amobarbital, nevirapine, primidone, rifabutin, rifampin, and St. John's wort).

20. Current use or anticipated need for treatment with drugs that are known CYP3A4 inhibitors (i.e. grapefruit juice, ketoconazole, nefazodone, itraconazole, miconazole, erythromycin, clarithromycin, telithromycin, verapamil, indinavir, saquinavir, ritonavir, nelfinavir, lopinavir, atazanavir, amprenavir, fosamprenavir and delavirdine)
21. Any of the following within 6 months prior to study drug administration: myocardial infarction, uncontrolled angina, coronary/peripheral artery bypass graft, symptomatic congestive heart failure, cerebrovascular accident or transient ischemic attack and 6 months for deep vein thrombosis or pulmonary embolism.

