### 3. Study Design

A Phase II, double-blind, 2 arm pilot randomised placebo controlled trial. 50 patients will be sequentially randomised 2:1 to Axitinib or placebo.

Inclusion criteria: Chemorefractory third-line metastatic CRC with US-assessable liver or other abdominal metastases that can have a baseline DCEUS baseline measurement.

Treatment arm: Axitinib monotherapy started in all patients at 5mg bd, and increased fortnightly by a dose level (See Table 4) as tolerated to a maximum dose of 10mg bd.

Control arm: Placebo (blinded) randomised 2:1 to Axitinib : placebo

Follow up: Outpatient monitoring at 2 weeks and 4 weeks post first dose then 4 weekly thereafter with RECIST restaging every 8 weeks. CEHPI at baseline, 2 weeks and 8 weeks for assessment of differential blood supply (CEHPI) with an optional visit at 48-72 hours post first dose. VEGF-PK samples at Day 15 & Day 28 and at 8 weeks and RECIST progression. At 8 weeks, after tumour CT RECIST assessments, conventional responders (CR/PR/SD) continue monotherapy. In non-responders (PD), monotherapy can be continued if patient chooses to continue and if tolerated. CT response assessments continue at 8 weekly intervals in all patients, with parallel 8 weekly DCE-US. CEHPI at baseline, optionally at 47-72 hours, 2 weeks, 8 weeks and at progression of disease.

[figure not shown]

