## 4. Subject Selection

### 4.1. Inclusion criteria

Patients must meet all of the following inclusion criteria for enrolment:

1. Histologically or cytologically confirmed adenocarcinoma of the colon or rectum with liver metastas(es) or other measurable lesion. At least one of which should not have had any focal therapy including radiofrequency ablation.
2. Evidence of uni-dimensionally measurable disease as defined by the Response Evaluation Criteria in Solid Tumours (RECIST).
3. 18 years of age or older.
4. ECOG performance status of 0 or 1.
5. Failed (or intolerant of ) at least 2 chemotherapy regimens in advanced disease and resolution of any acute toxic effects of prior therapy e.g. radiotherapy or surgical procedure to NCI CTCv4 grade  $\leq 1$ . No other alternative available effective treatment options.
6. Adequate organ function as defined by the following criteria:
7. Serum aspartate aminotransferase (AST; serum glutamic oxaloacetic transaminase [SGOT]) and serum alanine aminotransferase (ALT; serum glutamic pyruvic transaminase [SGPT])  $\leq 5$  x upper limit of normal (ULN).
8. Total serum bilirubin  $< 1.5$  x ULN
9. Serum albumin  $\geq 25$ mg/dl
10. Absolute neutrophil count  $\geq 1500/\mu\text{L}$
11. Platelets  $\geq 75,000/\mu\text{L}$
12. Haemoglobin  $\geq 9.0$  g/dL
13. Serum creatinine  $\leq 1.5$  x ULN
14. Signed and dated informed consent form
15. Willingness and ability to comply with scheduled visits, treatment plans, laboratory tests, and other study procedures

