## Appendix 5 Liver Ultrasound Protocol

The contrast agent used is SonoVue (Bracco SpA, Milan, Italy), which consists of a phospholipid shell containing the inert gas sulphur hexafluoride. The agent is prepared immediately prior to the examination by mixing 25 mg of the lyophilised powder with 5 ml of saline. 2.4 ml of the preparation is injected as an intravenous bolus via an antecubital vein.

After 4 hours of fasting, DCE-US scan is performed on each subject in the supine position using an iU22 ultrasound scanner (Philips Healthcare, Andover, MA) with a C5-1 curvilinear transducer. The probe is held still in the right intercostal space in order to visualise the porta hepatis. This allows simultaneous visualization of the hepatic artery (HA) and portal vein (PV) at a low mechanical index (0.06) imaging with non-linear pulse sequence in the form of power modulated pulse inversion. A 1 minute contrast/B-mode side-by-side cine loop is recorded with data acquisition starting immediately after the contrast bolus injection. A reading from a control artery (carotid or femoral) is taken to confirm the input function of the test. Cine loops are then transferred to a workstation for analysis.

QLAB software (Philips Healthcare, Andover, MA) is used to quantify contrast dynamics in the HAP and PV. Raw linear DICOM data is used for analysis. Regions of interest of equivalent sizes (5mm^2) are drawn over the HA and PV lumens. Time-intensity curves are obtained by computing the mean intensity of pixels comprised within the regions of interest against time. An example analysis is presented below:

**Figure 3: Time-intensity curve for hepatic artery (yellow), portal vein (red) using QLab software. Both have had modelling curves fitted to smooth the data. The calculated values for the DCE-HPI are shown in the box.**

TICs are fitted using a least square algorithm based on the Nelder-Mead method (Matlab, The MathWorks, Natick, MA) with a local density random walk function described by:

$$I(t) = AUC \frac{e^{\lambda}}{\mu} \sqrt{\frac{\mu}{(t-t_0)}} \frac{\lambda}{2\pi} \exp\left\{-\frac{1}{2}\lambda\left(\frac{\mu}{(t-t_0)} + \frac{(t-t_0)}{\mu}\right)\right\} + I_0$$

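### Section 4 eligibility conflicts with the rest of the protocol on ultrasound-assessable disease and the radiotherapy window, and sets albumin in a unit that makes the limit ineffective

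*Combined protocol and SAP*

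**What the plan says.** **Assessable disease.** Section 4.1 is the list of which every item must be met. Its no. 1 asks for colorectal adenocarcinoma "with liver metastas(es) or other measurable lesion", and no. 2 adds RECIST measurability. No item in 4.1 or 4.2 mentions ultrasound. Section 3, under its own inclusion label, asks for "US-assessable liver or other abdominal metastases that can have a baseline DCEUS baseline measurement", and the Trial Summary says the same. Section 2.2 makes PFS by 2-week CEHPI change (reduction above 20% versus 20% or less) a co-primary endpoint, although Section 9 describes the CEHPI comparison as secondary. In Appendix 5 the regions of interest for the index "are drawn over the HA and PV lumens", that is, over the hepatic artery and portal vein.

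**Radiotherapy.** Under a lead-in by which any listed item excludes, Section 4.2 no. 3 states "Palliative radiotherapy to non-target, metastatic lesions will be allowed provided it was completed within 4 weeks prior to study entry". In no. 1 a parenthesis says that prior pelvic radiotherapy "is allowed provided it is completed within 4 weeks prior to study entry". No. 4 excludes "Prior surgery within 4 weeks prior to study entry". Inclusion 5 requires acute effects of prior therapy, with radiotherapy given as an example, to have settled to grade 1 or less.

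**Albumin.** Section 4.1 no. 9 sets a lower limit for "Serum albumin" of 25 mg/dl. Appendix 1 lists albumin in g/dL, with a factor of 10 to g/L.

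**The concern.** Sites enrol from the numbered lists. If those lists disagree with the design section, contain a time window that can be read in two directions, or carry a limit in an unworkable unit, sites following the same protocol can make opposite decisions about the same patient.

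For the analysis, the first item matters most. The rationale for CEHPI in Section 1.2 is arterial supply to tumours growing in the liver. A patient with no abdominal disease can satisfy 4.1 and be randomised. That patient then either has no usable index or has one with no stated link to the tumour, yet may still be classed as a CEHPI responder or non-responder. The screening list in Section 6.1 contains no ultrasound and randomisation follows completion of screening. The Schedule of Activities puts the first CEHPI at predose Day 1, so nothing before randomisation catches the mismatch.

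The other two items concern who enters the trial and how far written safety criteria can be relied on.

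**Working it through.** No sample size, power or event figure underlies this point. The check is a comparison of passages and one unit conversion.

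**(a) Assessable disease.** Take a patient whose only measurable lesion is in the lung.

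| Source | Requirement | Met? |
|---|---|---|
| 4.1 no. 1 | liver metastasis or another measurable lesion | yes |
| 4.1 no. 2 | RECIST-measurable disease | yes |
| 4.2 nos. 1 to 21 | no ultrasound condition | not excluded on this ground |
| Trial Summary and Section 3 | liver or other abdominal metastases that ultrasound can assess | no |

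The patient is eligible under one part of the protocol and ineligible under another. Inclusion 15, on ability to comply with study procedures, does not make assessable disease a criterion.

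**(b) Radiotherapy window.** Apply the literal proviso (completed within the last 4 weeks) and the surgery exclusion to the same intervals.

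| Weeks since completion | Radiotherapy proviso satisfied (nos. 1, 3) | Surgery excluded (no. 4) |
|---|---|---|
| 1, 2, 3 | yes | yes |
| 5, 8, 26 | no | no |

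At every interval where the surgery rule excludes, the radiotherapy proviso permits, and the reverse. Literally, the proviso favours recent over remote treatment. Inclusion 5 points the other way in spirit, since acute toxicity is more likely to be unresolved soon after treatment. In addition, no. 3 is a permission placed in a list whose items are meant to exclude, so its presence has no clear effect.

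**(c) Albumin.** Inputs: 25 mg/dl (4.1 no. 9) and the factor of 10 from g/dL to g/L (Appendix 1).

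- 25 mg/dL ÷ 1000 = 0.025 g/dL.
- 0.025 g/dL × 10 = 0.25 g/L.

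To fail the criterion, a result reported in Appendix 1 units would have to be below 0.025 g/dL. The documents do not state what was intended, so two assumed readings show how wide the ambiguity is:

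- If 25 was meant in g/L: 25 ÷ 0.25 = 100 times the written limit.
- If 25 was meant in g/dL: 25 × 10 = 250 g/L, and 250 ÷ 0.25 = 1000 times the written limit.

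**The case against.** The ultrasound requirement is not missing from the protocol. The Trial Summary and Section 3 both state it as an inclusion criterion, so lung-only disease is already outside the described population. This stands: the defect is a failure to carry the condition into the operative list.

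On radiotherapy, exclusion 1 is about non-exposure to three drug classes, and radiotherapy appears only in a parenthesis. A patient with remote pelvic radiotherapy who has had all three classes does not strictly meet the exclusion. Surgery and radiotherapy may also properly have different windows. Both arguments have force. They show that the wording is ambiguous, and a proviso that is not satisfied still implies that the treatment is not allowed.

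On safety, inclusion 5 still requires acute toxicity to have resolved, and exclusion 17 lets the investigator exclude for a laboratory abnormality that adds risk. These are real but partial backstops.

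A reader might infer several stronger things that the documents do not support:

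- That the CEHPI contrast is diluted by a known amount. The share of patients without liver metastases is not given, and neither is how such patients would fall across the CEHPI groups.
- That much of the rectal cancer population is lost. The proportion with prior pelvic radiotherapy is not given, and exclusion 1 can be read otherwise.
- That two safety screens have been removed. The backstops above remain.
- That all CEHPI analyses must be confined to patients with liver metastases. Section 3 admits other abdominal disease, and Section 2.2 sets the CEHPI–RECIST correlation in the ITT population.

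**Conclusion.** The point holds as three inconsistencies in operative eligibility wording.

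(a) 4.1 admits patients whom Section 3 and the Trial Summary do not, and the CEHPI endpoint depends on the condition left out. Appendix 5 reads two vessels, so an index may be obtainable without a visible lesion. The loss is therefore one of interpretability and not necessarily of data.

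(b) Exclusions 1 and 3 literally favour recent over remote radiotherapy, fit poorly with inclusion 5, and contrast with exclusion 4. No view is taken on which window is right.

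(c) The written albumin limit is 0.25 g/L. That it screens out essentially nobody assumes that serum albumin is ordinarily in the tens of g/L; the documents give no distribution.

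The number of patients affected cannot be derived from the documents, and no power figure changes: Section 9.1 already says that 50 patients would not normally give adequate power. The items deserve correction because a literal reading gives wrong or contradictory enrolment decisions and the correction is cheap.

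**What to change.** - **4.1 no. 1:** carry over the Section 3 condition, namely liver or other abdominal metastases that can have a baseline contrast ultrasound measurement. Keep it as a capability. Requiring a completed scan for entry would mean moving the first CEHPI from predose Day 1 to before randomisation, which is a schedule change.
- **Optional analysis sentence:** add a sensitivity analysis of the CEHPI comparisons limited to patients with liver metastases at baseline, because the index is read only from the hepatic artery and portal vein. Leave the main CEHPI analysis populations as they are.
- **4.2 nos. 1 and 3:** the sponsor should reconcile the direction of the 4-week proviso with inclusion 5 and exclusion 4, and restate no. 3 so that it works within an exclusion list.
- **4.1 no. 9:** restate the albumin limit in g/dL or g/L as in Appendix 1, with the sponsor confirming the value.

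The cost is a few wording changes in Section 4 and, if wanted, one sentence in Section 9.2. The sensitivity analysis would use fewer patients and should be read as descriptive.

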## 6. Study Procedures

### 6.1 Screening

Demographic data, clinical history, response to previous treatments, functional status, imaging and histology results to date will be ascertained at baseline on a standard case report form (CRF). Patients will be eligible irrespective of k-ras mutation status.

The following screening procedures will be performed within up to 28 days prior to the start of treatment on study, unless otherwise stated:

- Patient signature on informed consent form (up to 28 days prior to treatment)
- Medical history including confirmation of histological diagnosis, history of other concomitant illnesses
- Demographics (including age, sex, and race)
- Physical examination including examination of major body systems, ECOG performance status, body weight, height (screening only), and vital signs (temperature, blood pressure, heart rate)
- Haematology performed within 7 days from treatment start
- Chemistry, CEA and CA19.9 performed within 7 days from treatment start
- Coagulation (APTT & INR) performed within 7 days from treatment start
- Thyroid Function Tests (free T3, free T4 and TSH)
- Pregnancy test (urine), if applicable, performed within 7 days from treatment
- Urinalysis by dipstick
- 12-Lead electrocardiogram
- Endoscopy or upper GI imaging, to exclude patients with suspected oesophageal varices and/or gastroduodenal ulcer.
- Assessment of concomitant medications and treatments
- Assessment of ongoing symptoms/events (serious adverse events must be recorded from time of signed consent)
- Study randomisation upon completion of all screening assessments
- Baseline (screening) tumour assessments require CT/MRI (no chest x-ray) of the chest and abdomen at the minimum. If the interval between any of the baseline tumour assessments and randomisation is >28 days, the baseline tumour imaging will be repeated.

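### Exclusions 1 and 3 state the 4-week radiotherapy condition backwards: they allow radiotherapy finished in the very period in which exclusion 4 bars surgery

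*Combined protocol and SAP*

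**What the plan says.** Three items of section 4.2 of the combined protocol and SAP use one time phrase.

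- **Item 1** requires prior exposure to three drug classes. A parenthesis then deals with earlier pelvic radiotherapy, including "adjuvant or neoadjuvant chemo-radiation therapy for resected rectal cancer is allowed provided it is completed within 4 weeks prior to study entry".
- **Item 3:** "Palliative radiotherapy to non-target, metastatic lesions will be allowed provided it was completed within 4 weeks prior to study entry".
- **Item 4:** "Prior surgery within 4 weeks prior to study entry".

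The list opens by saying that any item present excludes the patient. Item 4 fits that form. Item 3 is a permission, and so is the parenthesis in item 1.

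Other text that bears on the point:

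- Exclusion 2 bars patients with "Less than 6 months from completion of adjuvant chemotherapy to diagnosis or documentation of recurrent cancer".
- Inclusion 5 (section 4.1) requires failure or intolerance of "at least 2 chemotherapy regimens in advanced disease and resolution of any acute toxic effects of prior therapy e.g. radiotherapy or surgical procedure" to grade 1 or below. It gives no minimum time.
- Exclusion 17 leaves room for a condition that "in the judgment of the investigator would make the patient inappropriate for entry into the trial".
- Section 5.16 covers radiotherapy during the study only. It allows palliative treatment for pain at bone sites already present at baseline.
- Section 6.1 on imaging: "If the interval between any of the baseline tumour assessments and randomisation is >28 days, the baseline tumour imaging will be repeated".

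No section defines study entry, and none states a separate radiotherapy washout.

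**The concern.** A washout requires treatment to have ended at least a given time before entry. Items 1 and 3 require it to have ended no more than that time before entry. The surgery rule next to them runs the other way, so within one list the same words make a recent procedure disqualifying and recent radiotherapy acceptable.

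Two consequences follow. First, someone applying the text literally and someone assuming a washout would decide differently on the same recently irradiated patient. That affects eligibility checks, source verification and the classification of protocol deviations. The literal reader could also start a patient on study drug days after radiotherapy, with no minimum recovery time.

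Second, nothing requires radiotherapy to be finished before the baseline scan. A non-target lesion could be scanned, then irradiated, then followed against its pre-radiotherapy state. Under Appendix 6, unequivocal progression of non-target lesions is progressive disease, so the lesion's later course can bear on PFS.

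**Working it through.** The plan gives no figure to reproduce. The check is a comparison of the criteria, followed by date arithmetic.

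**1. The same dates under each rule, read literally**

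| Finished before entry | Radiotherapy (items 1, 3) | Surgery (item 4) |
|---|---|---|
| 1 week | meets the allowance | excluded |
| 8 weeks | outside the allowance, but meets no exclusion | not excluded |

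The two rules run in opposite directions.

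**2. Item 1, neoadjuvant chemo-radiation.** For resected disease the order is: radiotherapy ends, then resection, then entry. If radiotherapy ended in the 4 weeks before entry, the resection fell in those 4 weeks too, and item 4 excludes the patient. No eligible patient remains. This holds whatever entry means, because items 1 and 4 share the anchor.

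**3. Item 1, adjuvant chemo-radiation.** Two assumptions: its chemotherapy counts as adjuvant chemotherapy under exclusion 2, and 6 months = 26 weeks. Exclusion 2 then requires at least 26 weeks from completion to recurrence. Entry comes later still, after the two regimens in advanced disease that inclusion 5 requires. Completion therefore lies outside the window by at least 26 − 4 = 22 weeks.

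Steps 2 and 3 cover the named chemo-radiation groups. Item 1 also covers pelvic radiotherapy in general, which can fall inside the window.

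**4. How long after the baseline scan radiotherapy could end**

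Inputs:
- Day 0 is randomisation. Section 6.1 lists "Study randomisation upon completion of all screening assessments", so eligibility is settled by then.
- The scan is on day s, with −28 ≤ s ≤ 0 (section 6.1). The Schedule of Activities calls for a screening CT only if the last one is more than 28 days old, so a scan taken before consent can serve.
- Entry is on day −c. c = 0 if entry means randomisation. If it means consent, c can reach 28, since section 6.1 allows consent up to 28 days before treatment.
- Radiotherapy ends on day e, with e ≤ −c.

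Maximum of e − s = −c − (−28) = 28 − c.

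- Entry = randomisation (c = 0): 28 days.
- Entry = consent 14 days earlier: 28 − 14 = 14 days.
- Entry = consent 28 days earlier: 28 − 28 = 0 days.

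If the general section 6.1 rule (within 28 days before treatment start) also governs the scan, and treatment starts k days after randomisation with k = 0 to 7 (section 5.7), the earliest scan is day −28 + k. With c = 0 the maximum is then 28 − k, which is 28 to 21 days. The overall range stays 0 to 28.

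**5. With radiotherapy completed at least 4 weeks before randomisation**

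Now e ≤ −28, so the maximum of e − s is −28 − (−28) = 0 days, or −28 − (−28 + k) = −k, which is 0 to −7 days. Radiotherapy given before entry can no longer end after the baseline scan.

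**The case against.** The best reply is that this is a slip that nobody would act on. Patients come from one NHS Trust's clinics (section 5.1), staff will probably assume a washout, and step 2 itself shows that item 1 cannot sensibly be applied literally. Inclusion 5 and exclusion 17 already protect a patient who has not recovered. Endpoint harm is slight: item 3 covers non-target lesions only, Appendix 6 follows these as present or absent rather than measuring them, and inclusion 1 asks for at least one lesion without focal therapy. Section 5.16 also accepts radiotherapy to baseline bone sites after randomisation, so no pre-entry rule can ensure that study drug alone acts on non-target lesions.

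Most of that stands as to size. It does not rescue the wording. The written criterion is what eligibility is verified against, and neither inclusion 5 nor exclusion 17 supplies an interval.

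A reader might infer three stronger things, and the documents support none of them:

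- **That the rule shuts out everyone irradiated more than 4 weeks earlier.** Such patients fall outside a permission, but no stand-alone criterion excludes them.
- **That PFS is biased towards one arm.** Eligibility is settled before blinded randomisation, so any effect is non-differential.
- **That 28 days is the established gap.** It is the upper end, and requires entry to mean randomisation.

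**Conclusion.** The criteria are wrong as written and should be corrected. Items 1 and 3 admit recently irradiated patients by a condition that is the reverse of a washout and of item 4. That a washout was intended is a strong inference, resting on the surgery rule and on the near-empty window for the patients item 1 names. It is not stated anywhere.

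The main effects are on consistent eligibility decisions and on recovery before dosing. The effect on non-target assessment is minor and non-differential, with a possible overlap of 0 to 28 days depending on what study entry means. The 22-week figure for adjuvant patients depends on the two assumptions in step 3. The documents do not show how many of the 50 patients would be affected, and the planned sample size and error rates do not depend on the point.

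**What to change.** - Remove the timing conditions from items 1 and 3 and add one stand-alone exclusion: *Any radiotherapy (pelvic or palliative) completed less than 4 weeks prior to randomisation.*
- Keep the statement that earlier pelvic radiotherapy, and earlier palliative radiotherapy to non-target lesions, are allowed.
- Anchor item 4 to randomisation as well, the anchor that the imaging rule already uses.
- Ask the sponsor to confirm that 4 weeks is the intended interval.

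Two further changes should be avoided. An open-ended bar on radiotherapy to target lesions would make an implied restriction absolute. Moving the permission into section 4.1 would place it in a list where every item must be met.

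The cost is a few lines of section 4.2. A recently irradiated patient would wait up to 4 weeks, which is not trivial where section 9.1 expects PFS of 6-8 weeks. The wait may also mean repeating the baseline scan (28-day limit) and the laboratory tests (7-day limit).
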